7.7.3 AZD6738 adverse events of special interest

There are no AESI for AZD6738 which require additional data collection.

7.7.4 Olaparib adverse events of special interest:

Adverse events of special interest [AESI] are events of scientific and medical interest specific to the further understanding of olaparib's safety profile and require close monitoring and rapid communication by the investigators to AstraZeneca. Adverse Events of Special Interest for olaparib are the Important Potential Risks of MDS/AML, new primary malignancy (other than MDS/AML) and pneumonitis.

A questionnaire will be sent to any investigator reporting an AESI, as an aid to provide further detailed information on the event. During the study there may be other events identified as AESIs that require the use of a questionnaire to help characterize the event and gain a better understanding regarding the relationship between the event and study treatment.

7.7.5 Definitions of serious adverse event

An adverse event is considered “serious” if, in the view of either the investigator or Sponsor-Investigator, it results in any of the following outcomes:

- Death

If death results from (progression of) the disease, the disease should be reported as event (SAE) itself.

- A life-threatening adverse event

An adverse even is considered ‘life-threatening’ if, in the view of either the investigator [or sponsor], its occurrence places the patient or subject at immediate risk of death. It does not include an adverse event that, had it occurred in a more severe form, might have caused death.

- Inpatient hospitalization or prolongation of existing hospitalization for > 24 hours.
- A persistent or significant incapacity or substantial disruption of the ability to conduct normal life functions
- A congenital anomaly/birth defect
- Adverse events for malignant tumors reported during a study should generally be assessed as serious AEs. If no other seriousness criteria apply, the important medical event criterion should be used. Medical judgment on an individual event basis should be applied to clarify if non-serious AE or not. Please contact PI if this occurs for guidance.
- Important medical event

Any event that may not result in death, be life-threatening, or require hospitalization may be considered serious when, based upon appropriate medical judgment, they may jeopardize the patient and may require medical or surgical intervention to prevent one of the outcomes listed in this definition of “Serious Adverse Event”. Examples of such medical events include allergic bronchospasm requiring intensive treatment in an emergency room or at home; convulsions that do not result in inpatient hospitalization or the development of drug dependency or drug abuse.

Previously planned (prior to signing the informed consent form) surgeries should not be reported as SAEs unless the underlying medical condition has worsened during the course of the study. Preplanned hospitalizations or procedures for preexisting conditions that are already recorded in the patient’s medical history at the time of study enrollment should not be considered SAEs. Hospitalization or prolongation of hospitalization without a precipitating clinical AE (for example, for the administration of study therapy or other protocol-required procedure) should not be considered SAEs. However, if the preexisting condition worsened during the course of the study, it should be reported as an SAE. The causality of SAEs (their relationship to all study treatment/procedures) will be assessed by the investigator(s) and communicated to AstraZeneca.

7.7.6 Expected adverse events

An adverse event (AE) is considered “expected” if:

- For approved and marketed drugs or devices, those adverse events are described in the approved Package Insert (Label).
- For investigational new drugs or devices, those adverse events are described in the FDA Investigator’s Brochure.

7.7.7 Unexpected adverse events

An adverse event (AE) is considered “unexpected” if it is not described in the Package Insert, Investigator’s Brochure, in the protocol, or in the informed consent document

7.7.8 Suspected unexpected serious adverse reactions

A suspected unexpected serious adverse reaction is when an SAE occurs that is unexpected in the nature and/or severity compared with the information set out in Investigators Brochures.

7.7.9 Adverse event characteristics

7.7.9.1 CTCAE term

(AE description) and grade: The descriptions and grading scales found in the NCI Common Terminology Criteria for Adverse Events (CTCAE) version 5.0 will be utilized for AE reporting. All appropriate treatment areas should have access to a copy of the CTCAE version 5.0. A copy of the CTCAE version 5.0 can be down loaded from the CTEP web site. (<http://ctep.cancer.gov>)

7.7.9.2 Attribution of the AE

The investigator or co-investigator is responsible for assignment of attribution.

Definite – The AE is clearly related to the study treatment].

Probable – The AE is likely related to the study treatment].

Possible – The AE may be related to the study treatment.

Unlikely – The AE is doubtfully related to the study treatment.

Unrelated – The AE is clearly NOT related to the study treatment.

7.7.10 Reporting of serious adverse events

7.7.10.1 Reporting procedures for multi-site trials

All serious adverse events (SAEs) and unanticipated problems (UPs), regardless of causality to study drug, will be reported to the Principal Investigator and also to the Coordinating Center. All SAEs and UPs must be reported to the Coordinating Center within 24 hours of first awareness of the event. Events should be reported using the Coordinating Center’s SAE form as available in the study database. A copy of the SAE form as available in the study database should be sent to the Coordinating Center via fax at [contact] or via email to [contact] within 24 hours of the site’s knowledge of the event.

Follow-up information must also be reported within 24 hours of receipt of the information by the investigator.

All SAEs and UPs will be reported to the IRB per current institutional standards. The Coordinating Center will disseminate information regarding SAEs and UPs to the participating sites within 5 days of review of the information by the Coordinating Center's Principal Investigator (or designee in the event of extended absence) only in the case that the event(s) is believed to be related (i.e., possibly, probably, or definitely) to the study drug.

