7.7.12 Reporting of unanticipated problems

There are types of incidents, experiences and outcomes that occur during the conduct of human subjects research that represent unanticipated problems but are not considered adverse events. For example, some unanticipated problems involve social or economic harm instead of the physical or psychological harm associated with adverse events. In other cases, unanticipated problems place subjects or others at increased risk of harm, but no harm occurs.

Upon becoming aware of any incident, experience, or outcome (not related to an adverse event) that may represent an unanticipated problem, the investigator should assess whether the incident, experience, or outcome represents an unanticipated problem. The incident, experience or outcomes is considered unanticipated if it meets all of the following criteria:

1. Unexpected (in terms of nature, severity, or frequency);
2. Related or possibly related to participation in the research; and
3. Suggests that the research places subjects or others at a greater risk of harm than was previously known or recognized.

If the investigator determines that the incident, experience, or outcome represents an unanticipated problem, the investigator must report it to the Coordinating Center within 24 hours of the study team becoming aware of the problem.

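### The 5-day notice to sites in 7.7.10.1 tests unanticipated problems for relation to the study drug, while 7.7.12 defines them by relation to the research, so non-drug problems have no prompt route to the other sites

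*Combined protocol and SAP*

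**What the plan says.** Section 7.7.10.1 (Reporting procedures for multi-site trials) sets out reporting in two directions.

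- **Inward, without a filter.** "All serious adverse events (SAEs) and unanticipated problems (UPs), regardless of causality to study drug, will be reported to the Principal Investigator". The Coordinating Center receives the same reports, with a limit of 24 hours from first awareness. In addition, "All SAEs and UPs will be reported to the IRB per current institutional standards".
- **Outward, with a filter.** "The Coordinating Center will disseminate information regarding SAEs and UPs to the participating sites within 5 days of review" by the Coordinating Center's Principal Investigator or designee, but "only in the case that the event(s) is believed to be related (i.e., possibly, probably, or definitely) to the study drug".

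Section 7.7.12 (Reporting of unanticipated problems) explains that some incidents "represent unanticipated problems but are not considered adverse events". It gives an example: "some unanticipated problems involve social or economic harm instead of the physical or psychological harm associated with adverse events". It then lists three criteria, all of which must be met. The problem must be unexpected, it must be "Related or possibly related to participation in the research", and it must suggest a greater risk of harm than was previously known. Once the investigator decides that a problem qualifies, "the investigator must report it to the Coordinating Center within 24 hours of the study team becoming aware of the problem". Section 7.7.12 does not say when, or whether, the other sites are told.

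Section 7.3 (Data and Safety Monitoring) provides a second route. Data and patient safety issues are reviewed with the participating sites at least quarterly. Unanticipated problems are a listed topic, with no condition about the drug, and the report of the meeting goes to the DSMC each quarter.

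**The concern.** The two sections apply different relatedness tests to the same class of problem. Relation to the study drug is a natural filter for SAEs, because most SAEs in a metastatic cancer population say little about the treatment. It is a poor filter for UPs, which under 7.7.12 are linked to the conduct of the research and need not involve either drug. A problem with a study procedure, with the handling of genetic data, or with a shared data system could be judged to raise the risk to subjects and still fall outside the 5-day rule.

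What is at stake is how soon the other sites can act. The protocol names 4 academic centers, which share a sequencing laboratory, an electronic data capture system and common procedures, including optional shipment of drug to patients. A non-drug fault found at one site may therefore be present at another, and the protocol gives no prompt route by which the other sites would learn of it.

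**Working it through.** The point is textual. It depends on no error rate, power or sample size, and the plan states no figure to reproduce. The check is to follow a UP through the relevant sections.

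**1. Which test applies at each step**

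| Step | Section | Test applied to a UP | Timing |
|---|---|---|---|
| Classed as a UP | 7.7.12 | Unexpected; related or possibly related to the research; suggests greater risk | – |
| Site to Principal Investigator and Coordinating Center | 7.7.10.1, 7.7.12 | None (7.7.10.1 disregards drug causality) | 24 hours |
| To the IRB | 7.7.10.1 | None | Institutional standards |
| Coordinating Center to the other sites | 7.7.10.1 | Believed related to the study drug | 5 days from review |
| Review meeting with sites | 7.3 | None | At least quarterly |

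Only the fourth step carries a drug test.

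**2. Whether a UP can pass the first step and fail the fourth.** It can. Relation to the research is wider than relation to the drug. The social or economic harm named in 7.7.12 need not involve either drug, and the same holds for a privacy, procedural or data problem.

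**3. Whether the drug test can be applied to a UP that is not an adverse event.** Not with the tools the protocol supplies. The categories definite, probable and possible are defined in Section 7.7.9.2, and there only for an adverse event judged against study treatment. No attribution scale is given for any other kind of problem.

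**4. Whether another section supplies a prompt route.**

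- Section 7.3 reaches the sites, but on a quarterly cadence: 12 months / 4 = 3 months between meetings. More frequent meetings are tied to protocol activity, not to the occurrence of a UP. A site that cannot take part confirms in writing that it has reviewed the relevant data and safety issues.
- Section 9.6 has the safety assessment shared with investigators, but it speaks of adverse event, laboratory and SAE data and does not name UPs.

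**5. Size of the gap.** A drug-related UP goes to the sites within 5 days of review. A UP unrelated to the drug may wait until the next meeting, at most about 3 months if none is held sooner. The two clocks start at different points, since the 5 days run from the Coordinating Center's review and 7.7.10.1 sets no limit on when that review takes place. The comparison is therefore one of scale only.

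**The case against.** The strongest reply is that the protocol already shares these problems. All UPs leave the site within 24 hours whatever their cause, the IRB is told, and 7.3 puts UPs on the agenda of a regular meeting with the sites without a drug filter. This stands, and it limits the point to timing. A reader might infer from the word only in 7.7.10.1 that non-drug problems stay at the site where they arose, or that the other three centers receive no notice. The documents do not support either inference. The sentence sets when the 5-day duty applies; it does not forbid other sharing, and 7.3 provides for it.

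A second reply is that 7.7.10.1 sits under the heading on serious adverse events, uses the SAE form and speaks of events, so its filter may be meant only for UPs that are themselves adverse events. That is a fair reading, but it does not close the gap. Section 7.7.12, which would then govern the rest, deals only with reporting to the Coordinating Center and contains no rule for informing the other sites. On either reading the 7.3 meeting is the only named route.

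Three further inferences should be resisted.

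- Section 7.7.12 does not say that every UP falls outside the adverse events; it says that some types do.
- Nothing indicates what share of UPs would be unrelated to the drug, so a claim that most would be has no basis.
- It is tempting to argue that an unshared sequencing error would misassign patients between the DRPro and DRDef cohorts and so damage the primary analysis set. No such error is described. Both cohorts receive the same regimen, so it is not evident that a wrong label would meet the greater-risk criterion. Prior sequencing reports go to the coordinating site for review, and that center manages registration and data cleaning, so correction would not depend on a notice to the other sites.

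**Conclusion.** The mismatch is real and its consequence is modest. A UP that meets all three 7.7.12 criteria but is unrelated to the study drug has no prompt route to the other sites. It reaches them through the 7.3 review, a possible delay of up to about three months, against 5 days from review for a drug-related event. This assumes that 7.7.10.1 is applied as written, that meetings keep to the minimum quarterly cadence, and that the Coordinating Center does not choose to inform the sites sooner, which nothing prevents. The documents give no expected number of such problems, so the practical burden cannot be estimated. Severity is low: this is an inconsistency in subject-protection reporting, with no shown effect on the efficacy conclusions.

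**What to change.** In 7.7.10.1, split the dissemination sentence in two. Keep the rule that SAEs go to the participating sites when possibly, probably or definitely related to the study drug. Add that every UP meeting the three criteria in 7.7.12 goes to all participating sites within the same 5 days of review, whether or not it is related to the drug. Add a cross-reference to this rule in 7.7.12, and make clear that the review in 7.3 is in addition to the notice and does not replace it.

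The cost is one revised sentence with its cross-references, and a few more notices from the Coordinating Center. No data collection, sample size or analysis changes.

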7.7.10.2 Reporting procedures to AstraZeneca

All Serious Adverse Events (SAEs) occurring from the initial study treatment administration through 30 days following the last dose of the study treatment will be reported by the Coordinating Center to AstraZeneca. Any SAEs occurring after 30 days following the last dose of the study treatment that are believed to be related to study drug will also be reported to AstraZeneca.

For pharmacovigilance purposes and characterization, any case of MDS/AML or new primary malignancy occurring after 30 day follow up period should be reported to AstraZeneca Patient Safety whether it is considered a non-serious AE [e.g. non-melanoma skin cancer] or SAE, and regardless of investigator's assessment of causality or knowledge of the treatment arm.

Investigators will be asked during the regular follow up for overall survival if the patient has developed MDS/AML or a new primary malignancy and prompted to report any such cases. If patients who are gaining clinical benefit are allowed to continue study treatment post data cut off and/or post study completion then all SAEs must continue to be collected and reported to Patient Safety within the usual timeframe. Otherwise, after study treatment completion (i.e. after any scheduled post treatment follow-up period has ended) there is no obligation to actively report information on new AEs or SAEs occurring in former study patients.

The Coordinating Center will send the initial completed SAE Form within 24 hours of receipt via email to [contact].

If only limited information is initially available or an ongoing SAE changes in its intensity or relationship to the study drug, or if new information becomes available, a follow-up report will be generated and sent to AstraZeneca within 24 hours of receipt.

7.7.10.3 Reporting procedures to FDA

In this trial, serious, unexpected adverse events believed to be definitely, probably or possibly related to the study treatment will be reported to the Food and Drug Administration via the MedWatch 3500A. The Michigan IND/IDE Assistance Program (MIAP) will be responsible for reporting SAEs to the FDA that meet the reporting requirements in 21 CFR 312.32.

A copy of the MedWatch report must be faxed to AstraZeneca at the time the event is reported to the FDA. It is the responsibility of the investigator to compile all necessary information and ensure that the FDA receives a report according to the FDA reporting requirement timelines and to ensure that these reports are also submitted to AstraZeneca at the same time.

* A cover page should accompany the MedWatch form indicating the following:

- External Scientific Research (ESR)
- The investigator IND number assigned by the FDA
- The investigator's name and address

- The trial name/title and AstraZeneca ESR reference number

* Investigative site must also indicate, either in the SAE report or the cover page, the causality of events in relation to all study medications and if the SAE is related to disease progression, as determined by the principal investigator.

* Send SAE report and accompanying cover page by way of Email to [contact]

If a non-serious AE becomes serious, this and other relevant follow-up information must also be provided to AstraZeneca and the FDA

7.7.11 Routine reporting

All other adverse events- such as those that are expected, or are unlikely or definitely not related to the study participation- are to be reported annually as part of regular data submission.

7.7.12 Reporting of unanticipated problems

There are types of incidents, experiences and outcomes that occur during the conduct of human subjects research that represent unanticipated problems but are not considered adverse events. For example, some unanticipated problems involve social or economic harm instead of the physical or psychological harm associated with adverse events. In other cases, unanticipated problems place subjects or others at increased risk of harm, but no harm occurs.

Upon becoming aware of any incident, experience, or outcome (not related to an adverse event) that may represent an unanticipated problem, the investigator should assess whether the incident, experience, or outcome represents an unanticipated problem. The incident, experience or outcomes is considered unanticipated if it meets all of the following criteria:

1. Unexpected (in terms of nature, severity, or frequency);
2. Related or possibly related to participation in the research; and
3. Suggests that the research places subjects or others at a greater risk of harm than was previously known or recognized.

If the investigator determines that the incident, experience, or outcome represents an unanticipated problem, the investigator must report it to the Coordinating Center within 24 hours of the study team becoming aware of the problem.

7.7.13 Paternal exposure

Male patients should refrain from fathering a child or donating sperm during the study and for 6 months following the last dose.

Pregnancy of the patient's partners is not considered to be an adverse event. However, the outcome of all pregnancies (spontaneous miscarriage, elective termination, ectopic pregnancy, normal birth or congenital abnormality) should if possible be followed up and documented.

The outcome of any conception occurring from the date of the first dose until 6 months *after the last dose* should be followed up and documented.

Sites should notify the Coordinating Center for any patient partner pregnancies within 24 hours of knowledge of the pregnancy.

7.7.14 Genetics

As this study entails biopsy or circulating tumor genetic analysis at enrollment (unless already completed), genetic data will be analyzed and housed. The exploratory correlatives also will capture similar information.

7.7.15 Circulating correlative analytes

These will be collected per study calendar and are encoded to protect privacy

7.7.16 Specimen banking

Patient excess samples collected within this study (peripheral blood and excess tissue from biopsy returned from TEMPUS) will be retained at University of Michigan if the patient consented to specimen banking. Specimens will be stored indefinitely or until they are used up. If future use is withdrawn by the patient, best efforts will be made to stop any additional studies and destroy the previously obtained specimens.

Specimens being stored long-term for potential use not outlined in the protocol are subject to University of Michigan Policies Governing Tissue Sample Collection.

If a patient consented to the analysis of prior obtained tissue (e.g. prior biopsies before enrolment in study), they may be requested and housed at the University of Michigan.

7.7.17 Specimen management with AstraZeneca

As rarer subgroups are being identified in prostate cancer, the need to combine anonymized results across studies using the same analytical process is important. To minimize genetic exposure risks, any tissue shared will NOT be allowed to undergo large-scale (>30 genes) next generation sequencing. Again, patients may opt-out of sharing any tissue with AstraZeneca.

8. ROLES AND RESPONSIBILITIES

8.1 Sponsor Investigator

The Sponsor Investigator is responsible for performing the following tasks:

- Responsibility for the overall conduct of the study at all participating sites and for monitoring the progress of the study
- Reviewing and ensuring reporting of SAEs
- Reviewing data from all participating sites

